1. STUDY SUMMARY

TITLE The use of soluble fibre for the prevention of gestational diabetes among high-risk women. A pilot study.

AIMS The primary aim of this study is to evaluate the effect of a soluble fibre supplement in the development of gestational diabetes in women at high-risk. The secondary aim will be to evaluate the effect of the soluble fibre supplement on glycaemic control in high-risk women who develop gestational diabetes in early pregnancy.

DESIGN We plan to conduct a randomised single-blinded controlled study to evaluate the effect of the consumption of soluble fibre, from early to mid-pregnancy, on the incidence of gestational diabetes, insulin sensitivity, insulin secretion and metabolic control in GDM diagnosed participants.

POPULATION We will be studying women with diagnosis of gestational diabetes in previous pregnancies, (considered as high-risk) aged >18 years.

ELIGIBILITY Women over 18 years old with a history of gestational diabetes in previous pregnancies will be eligible to apply to this study. After first assessment, eligible women will be split according to their glycaemic status in women with and without early gestational diabetes.

TREATMENT Participants in the treatment arms will be taking 5 gr of Guar gum fibre supplement with meals three times a day (total daily 15 g). Participants in the placebo arms will be taking 5 gr of Cellulose three times a day (total daily dose 15 g).

DURATION Participants will be involved for 12 weeks.

OUTCOME MEASURES

In women with normal glucose tolerance at first assessment:

Primary outcome: Gestational diabetes (yes/no) at 28 weeks gestation.

Secondary outcomes: Insulin sensitivity and insulin secretion at 28 weeks gestation.

In women with early gestational diabetes (diagnosed at first assessment):

Primary outcome: Glycaemic control assessed the need of insulin treatment (yes/no)

Secondary outcomes: In women requiring insulin treatment: days-to-insulin and total daily insulin dose.

INTRODUCTION

GESTATIONAL DIABETES

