The beneficial effects of Guar gum on glycaemic control can possibly be explained through various mechanisms. Firstly, the impact on glycaemic control over the first two hours after consumption of food that possibly relates to the impact of soluble viscous fibres on delaying gastric emptying and slowing the digestion of carbohydrate in the small intestine. There is an additional benefit as Guar gum is fermented by the colonic microbiota to short-chain fatty acids which are recently been shown to have important benefits on beta-cell function presumably by stimulating the production of GLP1 (10).

THE ROLE OF HIGH-FIBRE DIETS IN THE PREVENTION AND TREATMENT OF GESTATIONAL DIABETES

In pregnancy, a high dietary fibre intake has been associated with a lower risk of GDM (11), and in healthy pregnant women, a low GI diet has been associated with lower birth weight and a lower

percentage of large for gestational age newborns (12). As for women who develop GDM, high-fibre diets have been associated with an improvement in perinatal outcomes such as macrosomia (12–14) and risk of C-section (13). In this group of women, high-fibre diets have also to significantly reduce the need to commence insulin treatment (13–15). Despite the documented benefits of a high-fibre diet, as women progress through pregnancy there are often changes in food perception and acceptability which makes compliance to specific diets often difficult. A dietary supplement that can be consumed with meals could be an attractive alternative for complying with the recommended dietary fibre requirements. In pregnancy, Guar gum has shown to reduce postprandial glycaemia after an OGTT (16) and in one study, long term consumption of 10 gr a day showed to decrease both fasting and postprandial glycaemia (17). Therefore, it could be considered in the treatment of women with gestational or who are at high risk of developing the condition.

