5. RANDOMISED CONTROLLED STUDY

Aim: To evaluate the effect of a soluble fibre supplement in glucose metabolism in pregnant women at high risk of developing gestational diabetes.

Study methodology: 12 week randomised, placebo-controlled, single-blinded study.

Intervention: Women will first be categorised according to their glycaemic status into two groups: GDM and glucose tolerant women. Afterwards, each group will be randomised into two groups and given either

- 1) Fibre supplement (Guar gum)
- 2) Placebo (Cellulose)

The participants will take the dietary supplement three times a day for 12 weeks. They will receive regular antenatal control according to NICE guidelines recommendations. Compliance will be addressed by weekly phone calls.

Number of volunteers: The number of participants will be arbitrarily define as no data of this type of intervention exists in this cohort. 40 participants will be recruited. Previous studies, outside pregnancy, have observed metabolic effects in samples of 15-40 subjects.

Recruitment: Women will be recruited in the antenatal clinic at Queen Charlotte and Chelsea's Hospital. An information sheet will be provided to eligible women in the first antenatal visit to explain the purposes of the study. Women who decide to take part will be asked to sign a consent form.

Randomisation: Initially women will be categorised according to glycaemic status in two cohorts: **Glucose tolerant** and **Early gestational diabetes (GDM)** cohort. Each of the two cohorts will then be independently randomised to either intervention or standard care using the sealed envelope website. Guar gum (intervention) and cellulose (placebo) will be provided in identical packed sachets.

STUDY OUTCOME MEASURES

PRIMARY OUTCOME MEASURES

- Glucose values at 0 and 120 minutes during an OGTT performed at 28 weeks in the glucose tolerant group.
- Glycaemic control assessed by need of insulin treatment (yes/no), days to insulin treatment and total insulin dose.

SECONDARY OUTCOME MEASURES

Assessing insulin sensitivity and insulin secretion at 28 weeks of pregnancy in the glucose tolerant cohort of women through validated indices using glucose and insulin (or C-peptide) values derived from the OGTT.

- Insulin sensitivity will be assessed using the Matsuda formula (18).
- Insulin secretion will be assessed by second-void fasting UCPCR as described by McDonald et al (19).

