- Women from the **Glucose tolerant cohort** will undergo a second OGTT. Blood and urine samples will be collected at 0 and 120 minutes. Glycaemic status will then be assessed with the endpoint being the diagnosis of GDM (yes/no). Insulin sensitivity and insulin secretion will be estimated using the same parameters as in the first visit. As part of the study, women will be weight to calculate BMI and gestational weight gain at 28 weeks gestation. The research team will have their last face to face visit with the participant to discontinue the intervention and answer any potential questions about the study.
- In women in the **Early GDM cohort**, glycaemic control will be assessed by the need of insulin treatment (yes/no) and in those requiring insulin the days-to-treatment (insulin) and total insulin dose will be recorded. Data will be obtained by reviewing medical records. As part of the study, women will be weight to calculate BMI and gestational weight gain at 28 weeks gestation. The research team will have their last face to face visit with the participant to discontinue the intervention and answer any potential questions about the study.

PROCEDURES

Women will be advised to fast for 10 hours the night before the oral glucose tolerance test. They will also be advised not to restrict carbohydrate ingestion the three days prior to the OGTT. At the antenatal clinic, blood samples will be collected at baseline (0 min) and at 120 min after the administration of an oral load of 75 g of glucose.

In the baseline sample other parameters will also be determined. Creatinine and HbA1c will measure in all participants and GAD antibodies will be requested in women in whom type 1 diabetes is suspected.

Serum insulin and C-peptide will be collected at 0 and 120 min during the OGTT.

Women will be advised to void their first urine before attending the antenatal clinic. Second-void fasting urine sample will be collected at 0 min during the OGTT. A second urine sample will be collected at 120 min. Urinary C-peptide will measure in these samples will be transfer to boric acid containers, the aliquoted into 1 ml cryotubes and stored at -80 °C until analysis. Serum creatinine will be collected at baseline (0 min) and measure in the central lab. The urinary C-peptide creatinine ratio (UCPCR) will be calculated using these data.

ASSESSMENTS

(i) Gestational diabetes

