Gestational diabetes will be diagnosed if fasting plasma glucose >5.6 mmol/L and/or 120 min plasma glucose >7.8 mmol/L after the glucose load administered in the OGTT. Women with fasting plasma glucose <5.6 mmol/L and 120 min plasma glucose <7.8 mmol/L will be classified as “Glucose tolerant”.

(ii) Insulin sensitivity

Insulin sensitivity will be assessed using the Matsuda index as originally described (18) (Equation 1) and using two modified Matsuda equations in which insulin is substitute by either serum or urinary C-peptide (21,22) (Equations 2 and 3).

Equation 1.

$$\text{ISOGTT} = 10,000 / \sqrt{[\text{FPG} \times \text{fasting insulin}] \times [\text{mean glucose} \times \text{mean insulin during OGTT}]}$$

Equation 2.

$$\text{ISOGTT-} \text{C-pep} = 500,000 / \sqrt{[\text{FPG} \times \text{FsC-pep}] \times [\text{mean glucose} \times \text{mean sC-pep during the OGTT}]}$$

Equation 3.

$$\text{ISOGTT-UCPCR} = 500,000 / \sqrt{[\text{FPG} \times \text{UCPCR}_{\text{pmol}/\text{mmol}}] \times [\text{mean glucose} \times \text{mean UCPCR during the OGTT}]}$$

* FPG= fasting plasma glucose. FsC= fasting serum C-peptide. FUCPCR= fasting urinary C-peptide creatinine ratio.

(iii) Insulin secretion

[figure not shown]
Insulin secretion will be estimated by the UCPCR obtained using the fasting second-void urine sample, as it is strongly correlated with serum insulin, serum C-peptide (19) and 24-h urinary C-peptide (20).

Insulin response will be estimated using the UCPCR calculated with 120 min post-OGTT urine sample, as it is strongly correlated with the C-peptide and insulin area under the curve (19).

(iv) Need of insulin treatment, Days to insulin treatment and Total insulin dose

Medical records of women in the Early GDM cohort will be reviewed in order to determine the need of insulin treatment (yes/no) at 28 weeks gestation. In women requiring insulin treatment at any time during follow up, days-to-insulin treatment, calculated from randomisation day to the day insulin treatment is prescribed, and total insulin dose, calculated as the total dose of insulin international units (IU) divided by weight in Kg (insulin UI/Kg), will be recorded

Timeline for randomised controlled study

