9. STATISTICS AND DATA ANALYSIS

Data handling and analysis will be carried out by SPSS version 20.0 version.

No power calculation to decide sample size will be used. The number of participants has been arbitrarily defined, as it is a pilot study. We aim to recruit 40 women.

Before randomisation, women will be categorised according to their glycaemic status in two cohorts: Glucose tolerant and GDM. Each of these two cohorts will be randomly allocated into the

intervention (soluble fibre supplement) and control (placebo) group. Randomisation will be by sealed envelopes. Participants but not researchers will be blinded as to the type of intervention prescribed.

Differences between group in each cohort will be assessed using Student t test or Mann-Whitney U test for numeric variables depending on distribution; χ^2 will be used for categorical variables.

In the Glucose tolerant women cohort:

For the primary outcome, GDM (yes/no), logistic regression analysis will be performed.

For the secondary outcomes, insulin sensitivity and insulin secretion, linear regression analysis will be performed.

In the early GDM cohort:

For the primary outcome, need for insulin treatment (yes/no), logistic regression analysis will be performed. Additionally days-to-treatment analysis will be performed for those participants starting insulin therapy during follow up.

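### In the early-GDM cohort, days-to-insulin and insulin dose are assessed only in women who start insulin, so the arm comparison can be diluted or reversed if the fibre changes who starts

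*Combined protocol and SAP*

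**What the plan says.** **Days to insulin.** Section 9, early GDM cohort: "Additionally days-to-treatment analysis will be performed for those participants starting insulin therapy during follow up". Section 6, Assessments (iv), defines the measure as "days-to-insulin treatment, calculated from randomisation day to the day insulin treatment is prescribed", for women who need insulin at any point in follow-up.

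**Dose.** The Study Summary lists "In women requiring insulin treatment: days-to-insulin and total daily insulin dose". Section 6, 4th visit, says "in those requiring insulin the days-to-treatment (insulin) and total insulin dose will be recorded". Section 9 names no analysis for dose. The only method that could apply is its general rule for numeric variables, a t test or Mann-Whitney U test.

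**Non-starters.** No section censors women who never start insulin, names a survival method, or gives these women a dose value.

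**The analysis not limited to starters.** Section 9: "For the primary outcome, need for insulin treatment (yes/no), logistic regression analysis will be performed".

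**Status and definitions differ between sections.**
- Section 5 puts all three measures under primary outcomes, with no restriction to starters: "Glycaemic control assessed by need of insulin treatment (yes/no), days to insulin treatment and total insulin dose". The Study Summary makes days and dose secondary. Section 9 names only the yes/no outcome as primary.
- Dose is a daily total in the Study Summary. In Section 6, Assessments (iv), it is "calculated as the total dose of insulin international units (IU) divided by weight in Kg".
- Assessments (iv) determines need for insulin at 28 weeks, but takes days and dose from women on insulin at any time in follow-up. A woman who started and stopped could count in one set and not the other.

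**The concern.** Randomisation makes the two arms comparable as a whole. It does not do so for a subgroup picked out by something that happens afterwards and that the treatment may influence. Starting insulin is such an event. The Introduction gives the protocol's own reason to expect an effect on it, saying that "high-fibre diets have also to significantly reduce the need to commence insulin treatment".

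A woman whom the fibre spares from insulin is the clearest success in this cohort, yet she contributes nothing to days or dose. If the fibre mainly spares women who would have started late on small doses, the remaining fibre-arm starters are the earlier, more severe cases. The fibre could then seem to make no difference, or to bring insulin forward and raise the dose, while reducing the need for it. Readers using the pilot to plan a larger trial could draw the wrong conclusion.

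**Working it through.** There is no figure in the plan to reproduce: the sample of 40 is called arbitrary, and no insulin rate, effect size, alpha or power is given. Follow-up of 12 weeks (Study Summary and Section 5) is taken as t = 84 days. **All rates, hazard ratios, start days and doses below are assumptions.**

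**1. Proportional effect, constant hazard.** Let L be the hazard of starting insulin and S = exp(−L·t).
- Mean days among starters = 1/L − t·S/(1 − S)
- Mean insulin-free days to day 84, all women = (1 − S)/L

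Example with 50% of placebo women starting: L = ln 2/84, so 1/L = 121.2.
- Placebo: starters 121.2 − 84 = 37.2 days; all women 0.5 × 121.2 = 60.6 days.
- Fibre, hazard ratio (HR) 0.5: S = 0.707 and 1/L = 242.4. Starters 242.4 − 84 × 0.707/0.293 = 39.6 days; all women 0.293 × 242.4 = 71.0 days.

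| Placebo women starting | HR | Difference, starters only (days) | Difference, all women (days) |
|---|---|---|---|
| 30% | 0.5 | 1.2 | 6.3 |
| 50% | 0.5 | 2.4 | 10.4 |
| 70% | 0.5 | 4.0 | 14.3 |
| 30% | 0.7 | 0.7 | 3.7 |
| 50% | 0.7 | 1.4 | 6.0 |
| 70% | 0.7 | 2.4 | 7.9 |
| any | 1 | 0 | 0 |

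These are different quantities; the first leaves out the women who avoid insulin. At HR 0.5 the starters-only figure is smaller by 72% to 81%. If women's underlying hazards vary (gamma frailty with variance 0.5, 1 or 2, 50% starting on placebo, HR 0.5), the differences are 3.3, 3.9 and 4.5 days in starters against 10.2, 9.9 and 9.0 in all women. The gap is narrower but at least half is still lost.

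**2. Selective prevention, 50% starting on placebo.** Split would-be starters at their median time, −ln(0.75)/L = 34.9 days. The earlier half (25% of women) has mean 121.2 − 34.9 × 0.75/0.25 = 16.6 days. The later half has mean 2 × 37.2 − 16.6 = 57.8 days.
- *25% of earlier and 50% of later starts prevented:* 0.1875 + 0.125 = 31% start. Starters' mean = (0.1875 × 16.6 + 0.125 × 57.8)/0.3125 = 33.1 days, down from 37.2. Insulin-free time gained = 0.0625 × (84 − 16.6) + 0.125 × (84 − 57.8) = 7.5 days. The sign is reversed.
- *50% prevented in both halves:* starters-only difference 0.0; gain 0.125 × 67.4 + 0.125 × 26.2 = 11.7 days.
- *Opposite pattern, 50% of earlier and 25% of later:* starters' mean = (0.125 × 16.6 + 0.1875 × 57.8)/0.3125 = 41.3 days, which is the right direction.

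**3. Dose.** Assume mean dose 0.62 IU/kg in the more severe half of starters and 0.38 in the milder half, with 25% and 50% of starts prevented respectively. Starters' mean goes from 0.50 to (0.1875 × 0.62 + 0.125 × 0.38)/0.3125 = 0.52 IU/kg. With non-users at 0, the all-women mean goes from 0.25 to 0.16.

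**4. A case where the fibre helps every starter.** Assume 25% of women are severe starters (day 21, 0.6 IU/kg) and 25% mild (day 60, 0.2 IU/kg). Fibre prevents 80% of mild starts, delays all other starts by 3 days and cuts dose by 5%.
- Starters' days: (0.25 × 21 + 0.25 × 60)/0.5 = 40.5 against (0.25 × 24 + 0.05 × 63)/0.30 = 30.5.
- Starters' dose: 0.40 against 0.51 IU/kg.
- All women: insulin-free time 62.3 against 68.0 days; dose 0.200 against 0.152 IU/kg.
- With 50% of mild starts prevented, starters' days are 40.5 against 37.0. With 20%, they are 40.5 against 41.3 and dose is essentially unchanged, so there is no reversal of days.

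**5. Small numbers.** Assume 5 or 10 women per arm in this cohort, 50% starting on placebo and HR 0.5. Expected starters are 2.5 and 1.5 (5 per arm) or 5.0 and 2.9 (10 per arm). In 100,000 simulated trials the starters-only difference pointed the wrong way in 47% and 45% of the trials where it could be computed, against 26% and 19% for insulin-free time in all women. It could not be computed in 20% and 3%, because an arm had no starters.

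**The case against.** The strongest points on the other side are these.

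- **Reversal is conditional.** It needs later or milder starters to be prevented more often. The opposite pattern exaggerates the delay without changing its direction, and under a constant hazard with a proportional effect the sign does not reverse on average. This stands. It limits the claim to what can happen; dilution needs no such selectivity.
- **No section says both primary and starters only.** Section 5 ranks days and dose as primary without the restriction; where the Study Summary restricts them, they are secondary. This is right, and the status conflict is partly a separate drafting matter. The restriction still governs the only days analysis that Section 9 describes.
- **The comparison is partly inferred.** Section 9 names no test for days and no analysis for dose. This stands, most of all for dose. But no method applied to starters alone can bring back the women left out.
- **The Introduction's evidence on insulin need concerns high-fibre diets.** For guar gum in pregnancy it reports only glycaemia. This is fair, but reduced insulin need is the effect that this cohort is set up to look for.
- **This is a small pilot, and the yes/no result would be reported alongside.** That limits the harm and explains the low power. It does not justify the choice of population, and the two results could contradict each other on the page.

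**Conclusion.** The concern holds and should be fixed. As written, days-to-insulin and, by implication, dose would be compared within a subset formed after randomisation by an event that the fibre is meant to influence. With HR 0.5 and 30% to 70% of placebo women starting, the starters-only difference is 1.2 to 4.0 days, against 6.3 to 14.3 insulin-free days in all women. Reversal of days or dose is possible, but only if the fibre selectively spares the later or milder starters. These sizes rest on assumed rates, effects and doses, because the documents give none; the defect in the comparison does not depend on them. If the fibre has no effect on who starts, there is no bias. The yes/no logistic regression is not affected.

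**What to change.** - **Days.** Analyse time from randomisation to first insulin prescription in all randomised early-GDM women, censoring non-starters at the 28-week visit or last contact. Report Kaplan-Meier curves with a log-rank test, and a hazard ratio or a difference in restricted mean insulin-free time, with 95% CI. A hazard ratio has no finite estimate if an arm has no starters. With an assumed 29% starting on fibre, the fibre arm has none with probability 0.707^10 = 3% at 10 per arm and 0.707^5 = 18% at 5, so say in advance what will be reported then.
- **Dose.** Compare all women with non-users counted as 0, for example with a rank-based test, or label dose among starters as descriptive only.
- **Starters-only days.** Keep as a descriptive summary.
- **Wording.** Reconcile the Study Summary, Section 5 and Section 9 on whether days and dose are primary or secondary. Reconcile the Study Summary and Section 6 on how dose is defined. In Assessments (iv), settle whether need for insulin means at 28 weeks or at any time.

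The cost is revised text in Sections 6 and 9 and a recorded censoring date (and a 0 dose, if used) for women not on insulin. The 28-week visit already exists, so no visit or test is added. Scoring dose as 0 partly repeats the yes/no outcome. The change does not supply power: a log-rank test has about 16% at 10 per arm with HR 0.5 and 50% starting on placebo.

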10. REGULATORY ISSUES

ETHICS APPROVAL

The study has obtained approval from the Bromley Research Ethics Committee (REC) and Health Regulator Authority (HRA). The study must also receive confirmation of capacity and capability from each participating NHS Trust before accepting participants into the study or any research activity is carried out. The study will be conducted in accordance with the recommendations for physicians involved in research on human subjects adopted by the 18th World Medical Assembly, Helsinki 1964 and later revisions.

CONSENT

Consent to enter the study must be sought from each participant only after a full explanation has been given, an information leaflet offered and time allowed for consideration. Signed participant consent should be obtained. The right of the participant to refuse to participate without giving reasons must be respected. After the participant has entered the study the clinician remains free to give alternative treatment to that specified in the protocol at any stage if he/she feels it is in the participant's best interest, but the reasons for doing so should be recorded. In these cases, the participants remain within the study for the purposes of follow-up and data analysis. All participants are free to withdraw at any time from the protocol treatment without giving reasons and without prejudicing further treatment.

CONFIDENTIALITY

The Chief Investigator will preserve the confidentiality of participants taking part in the study and is registered under the Data Protection Act. After consent is obtained, a letter will be sent to the

participant's GP to inform that she will be taking part in the study. Personal data will only be stored in Trust's files. A specific study code will be used to store anonymised data at Imperial College's Department of Investigative Medicine. Data and all appropriate documentation will be stored for a minimum of 10 years after the completion of the study, including the follow-up period. Blood samples will be handled by NHS Trust regular procedures. Urine samples, collected for research purposes will be stored at Imperial College's Department of Medicine until the study is concluded. After analysis, samples will be disposed in accordance with the Human Tissue Authority's Code of Practice.

INDEMNITY

Imperial College holds negligent harm and non- negligent harm insurance policies which apply to this study.

SPONSOR

Imperial College London will act as the main sponsor for this study. Delegated responsibilities will be assigned to the NHS trusts taking part in this study.

FUNDING

The Department of Investigative Medicine, Imperial College, will be funding this study.

AUDITS AND INSPECTIONS

The study may be subject to inspection and audit by Imperial College London under their remit as sponsor and other regulatory bodies to ensure adherence to GCP and the NHS Research Governance Framework for Health and Social Care (2nd edition).

GUAR GUM FIBRE SOURCING

Sachets containing 5 gr of partially hydrolised Guar gum fibre will be sourced by Nestle. The product will be stored at room temperature at Imperial College's Department of Medicine.

PLACEBO (CELLULOSE) SOURCING

Cellulose will be sourced by Nestle. The product will be stored at room temperature at Imperial College's Department of Medicine.

